Appendix G: Postextubation Management Worksheet

Appendix H: Data Safety Monitoring Board Charter

 Appendix H1: DSMB Agreement

 Appendix H2: DSMB Status Report

 Appendix H3: DSMB Meeting Report

1 ABBREVIATIONS

AE	Adverse Event
ACV	Assist Control Ventilation
ALI	Acute Lung Injury
ARDS	Acute Respiratory Distress Syndrome
BiPAP	BiLevel Positive Airway Pressure
CCU	Coronary Care Unit
CHF	Congestive Heart Failure
COPD	Chronic Obstructive Pulmonary Disease
CPAP	Continuous Positive Airway Pressure
DSMB	Data Safety Monitoring Board
FiO2	Fraction of inspired oxygen
GMC	Grant Medical Center
HCO3	Bicarbonate
HFNC	Heated High Flow Nasal Cannula oxygen
HIPAA	Health Insurance Portability and Accountability Act
ICU	Intensive Care Unit
LAR	Legally Authorized Representative
LOS	Length of Stay
MICU	Medical Intensive Care Unit
MRN	Medical Record Number
MV	Mechanical ventilation
NIV	Non-invasive ventilation
OHRI	OhioHealth Research Institute
OHSP	Office of Human Subjects Protections
PaO2	Partial pressure of oxygen
PaCO2	Partial pressure of carbon dioxide
PHI	Protected Health Information
PSV	Pressure Support Ventilation
REDCap	Research Electronic Data Capture
RSBI	Rapid Shallow Breathing Index
SAE	Serious Adverse Event
SBT	Spontaneous Breathing Trial
SICU	Surgical Intensive Care Unit
SIMV	Synchronized Intermittent-Mandatory Ventilation
VAP	Ventilator-Associated Pneumonia

2 STUDY SUMMARY

2.1 Protocol Summary Table

Protocol Title & Number	Exploratory trial to improve postextubation management for patients at risk for extubation failure IRB# 1332767
Study Short Title	GMC – [name] – Postextubation Management Pilot
Research Method	Prospective Interventional
Therapeutic Area	Pulmonary/Critical Care
Department	Intensive Care Unit, Critical Care Unit, 4 East
Study Description	This is an exploratory study designed to gather baseline information to determine the effectiveness of a standardized postextubation management protocol in a subset of patients at risk for reintubation.
Primary Endpoints	
• Proportion of patients that require reintubation within 72 hours• Association between reintubation rates and patient demographics or characteristics
Secondary Endpoints	
• Length of stay (ICU and total)• Ventilator time• In-hospital mortality• In-hospital adverse event rate• 30-day readmission rate
Prospective Cohort Study Population ^a	This study will include up to 40 mechanically ventilated, adult patients considered at-risk for re-intubation. See Section 6.3 . for detailed inclusion criteria.
Intervention(s)	
• Early NIV via BiPAP• High Flow Nasal Cannula breaks from NIV• Wean after 24 hours
Duration	Intervention Duration – Approximately 24 hours Study Duration – 3 months Participant Duration- total hospital stay, estimated at 14.1 ± 16.9 days (American Association for the Surgery of Trauma, 2011).

^a Data for this study will be compared to a historical control cohort, comprising mechanically ventilated, high-risk patients who underwent standard of care postextubation management.

2.2 Study Diagram

3 INTRODUCTION

3.1 Study Rationale

It is clinically challenging to predict when patients can be successfully removed from mechanical ventilation (MV). Liberating high-risk patients such as the elderly and those with complex, chronic cardiac or pulmonary diseases from MV is particularly challenging.

Evidence from randomized trials and meta-analyses suggests that the type of postextubation supportive care provided, such as oxygen delivery via nose or mouth, may affect the risk of reintubation. However, it is unclear which of many possible postextubation management protocols results in the best patient outcomes, particularly for this subset of high-risk patients.

The purpose of this exploratory study is therefore to assess a standardized combined protocol of postextubation oxygen delivery consisting of early, alternating NIV with HFNC over 24 hours following extubation. NIV and HFNC are both currently provided to patients at Grant Medical Center as standard of care, based on clinician judgement; however, the timing and nature of the methods are variable.

The purpose of this exploratory study is therefore to obtain preliminary data that will be used to plan a larger, randomized control trial designed to explicitly compare a standardized postextubation management protocol to other standard of care protocols in patients that are traditionally at high risk for extubation failure.

3.2 Background

Intensive Care Unit (ICU) patients that are on mechanical ventilation (MV) are assessed regularly to determine whether they will be able to successfully breathe on their own if removed from the ventilator. This determination is important, as keeping patients on the ventilator longer than necessary can result in lung injury, infections, and increased length of stay (Zein et al., 2016; Karthika et al., 2016). Conversely, removing a patient from the ventilator too soon, when the patient cannot breathe unsupported, can result in multiple complications that require the patient to be placed back on the ventilator and may increase morbidity and mortality (Karthika et al., 2016).

Predicting whether or not a patient can be successfully liberated from mechanical ventilation is challenging, and approximately 12-14% of patients who undergo planned extubation require reintubation within 48-72 hours (Thille et al., 2013). Several risk factors have been associated with reintubation, including a weak cough and frequent suctioning (Esteban et al., 2002), rapid shallow breathing index >58 breaths/min/L, positive fluid balance during the 24 hours preceding extubation, and pneumonia as the reason for initial intubation (Frutos-Vivar et al., 2006). Patients who are ≥ 65 years of age with severe chronic cardiac or respiratory disease appear to be at particularly high risk for extubation failure, with reintubation rates ranging from 35% to 67% (Thille et al., 2013; Robiquet et al., 2006). Given the subsequent extubation failure in a high percentage of patients deemed appropriate for extubation, a number of studies have been conducted to determine whether postextubation management can be optimized in order to reduce the likelihood that a patient will need to be reintubated.

Postextubation management typically includes oxygenation via facemasks or nasal cannula, and airway clearance using suctioning, bronchodilator therapy, and/or diuresis. Alternative approaches include the use of noninvasive ventilation (NIV) such as bi-level positive airway pressure (BiPAP) or continuous positive airway pressure (CPAP) and/or high flow nasal cannula oxygenation (HFNC). At OhioHealth Grant Medical Center, postextubation oxygen therapy is based solely on clinician discretion and there is limited data to support whether one approach is better than another. Published literature for trials designed to determine the clinical benefit of varying postextubation management protocols are difficult to interpret due to a lack of standardized approach to oxygenation and ventilator support following extubation, heterogeneity in the populations studied, and variable duration of therapy. Specifically, there is some evidence that NIV may prevent postextubation respiratory failure (Nava et al., 2005; Ferrer et al., 2006; El-Soh et al., 2006; Ferrer et al., 2009; Burns et al., 2014; Khilnani et al., 2011). However, results from other trials indicate that NIV may be ineffective or even potentially harmful if it is not initiated until after the onset of postextubation respiratory failure (Esteban et al., 2004; Keenan et al., 2002). Similarly, trials exploring the effect of HFNC on reintubation indicate that outcomes are highly dependent on patient population of interest, as HFNC has been shown to be equivalent to NIV in preventing reintubation in post-cardiac surgery patients (Stéphan et al., 2015) but inferior to NIV in patients intubated following abdominal surgery (Jaber et al., 2016).

Few studies explicitly compare HFNC to NIV in the high-risk patient population of interest and no trials have evaluated a combined postextubation management protocol. In the largest randomized control of HFNC vs. NIV to-date, Hernández et al. (2016) compared HFNC with NIV immediately after planned extubation in patients considered at high risk for reintubation and found that HFNC administered for 24 hours after extubation resulted in similar rates of reintubation compared to NIV (23% vs. 19%, respectively). This trial suggests that HFNC and NIV are equivalent in high-risk patients, in terms of safety and efficacy.

The purpose of this study is to evaluate a standardized postextubation management protocol consisting of intermittent BiPAP during the day (2 hours on, 2 hours off), BiPAP throughout the night, and HFNC administered during BiPAP breaks. The study investigator hypothesizes that patients who are placed on a combined protocol of intermittent NIV and HFNC following extubation may be at lower risk for reintubation.

4 SPECIFIC AIMS

The purpose of this study is to establish baseline data regarding the institutional reintubation rate in a specific, high-risk patient population of interest and to determine the preliminary effectiveness of a standardized intermittent NIV/HFNC protocol in patients considered high risk for reintubation. This is a prospective, non-randomized exploratory trial with the following specific aim(s):

Aim 1. Compare reintubation rates (within 72 hours) between patients that undergo a standardized, intermittent NIV/HFNC protocol and a historical control cohort.

Aim 2. Determine whether reintubation rates differ as a function of age, gender, co-morbidity, reason for intubation, service line/operative status, or modified RSBI.

Secondary aims include calculating length of stay (ICU and total hospital), total ventilator time, in-hospital mortality rate, adverse event rates, and 30-day readmission rate. The overall demographics of the interventional group will also be compared to the historical control cohort.

5 STUDY POPULATION AND SAMPLE SIZE

There are approximately 3-4 patients per business day (Monday through Friday) that require mechanical ventilation at OhioHealth Grant Medical Center, resulting in approximately 80 patients per month. An estimated 30% of these patients are high risk, resulting in an estimated 24 high-risk patients per month.

A historical control cohort will consist of up to 80 randomly selected high-risk patients that underwent planned extubation in an OhioHealth Grant Medical Center Intensive Care Unit prior to initiation of the prospective cohort.

For the prospective, interventional cohort we plan to consent all adult mechanically ventilated patients that meet pre-screening criteria in order to obtain a final sample size of 40 enrolled patients who meet all criteria on the day of extubation. We anticipate this will result in up to 240 patients consented and 40 patients enrolled over approximately 12 weeks; however, this time period can be extended if needed to obtain 40 patients in the final data set.

See [Section 6.3](#) for detailed inclusion/exclusion criteria.

6 STUDY DESIGN

6.1 Overall Design

We propose a prospective, non-randomized exploratory study to obtain baseline data on reintubation rates for patients enrolled into a standardized postextubation management protocol compared to a historical control cohort consisting of mechanically ventilated high-risk patients that received clinician-directed, non-standardized postextubation management. We do not have current data demonstrating the specific type(s) of postextubation oxygen delivery but estimate that few patients receive combined BiPAP and HFNC. We will, however, record the types of postextubation oxygen management for the historical control cohort so that any subsequent statistical analyses can account for this potential confound.

6.2 Study Groups

Historical Control Group (Group 1): The historical control group will consist of up to 80 mechanically ventilated patients with documented presence of one or more chronic cardiac or pulmonary conditions that underwent planned extubation during the study period and meet all inclusion criteria outlined below.

Interventional Group (Group 2): The interventional group will consist of up to 40 patients for whom the LAR provides informed consent and who meet all study eligibility criteria.

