6.3 Participant Identification Procedures and Eligibility Criteria

6.3.1 Historical Control Group:

Reintubation rates are tracked at the institutional level as part of quality assessments; a delegated member of the study team will utilize this patient list to generate a study-specific subset of high-risk patients who were mechanically ventilated between February and October 2019. This list will be screened for the inclusion/exclusion criteria below by a delegated member of the study team. The study statistician or designee will then use a random number generator to generate a final group of 80 patients that meet inclusion criteria.

Inclusion Criteria

1. Age ≥ 18 years
2. Chronic cardiac or pulmonary condition
 - o COPD, history of based on any documentation notes
 - o CHF, history of based on any documentation notes
 - o Positive fluid balance, defined as a positive number when calculating fluid input minus fluid output over the approximate 24-hour-period prior to extubation
3. Documented modified RSBI between 58-105 on the day of extubation

Exclusion Criteria

1. Patients receiving comfort care or terminal extubation
2. Home ventilator, based on any documentation notes
3. Only primary extubations will be included (i.e., if the patient list query identifies multiple mechanical ventilations, only the primary encounter/event will be included)

6.3.2 Prospective Group:

An EMR-based report of all patients that have been on mechanical ventilation (MV) at Grant Medical Center for at least 24 hours will be generated daily (Monday through Friday), per standard procedure. Eligibility determination for this cohort will be conducted by a delegated member of the study team across two time points: pre-screening to determine eligibility to approach for consent, and eligibility on the day of extubation to determine enrollment eligibility (Appendix A). Only patients meeting all required eligibility criteria above will be enrolled to the study; any PHI collected for patients that are not subsequently enrolled will be destroyed after non-eligibility determination.

Pre-Screening Criteria:

1. No home ventilator, based on any documentation notes
2. Not scheduled for terminal extubation/comfort care
3. Has not had a failed extubation during the current hospital stay
4. Has not previously participated in the current trial

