5. Any other reason, at the discretion of the study team/clinical care staff, that should preclude the LARs being approached. These include, but are not limited to, facial trauma or other severe injuries that make extubation unlikely or that would make BiPAP contraindicated. Because patients will be screened daily, it is possible that a patient that fails pre-screening earlier in the stay may be eligible for enrollment later in their stay. This is okay.

Day of Extubation Criteria

1. Patient/LAR provided informed consent
2. Documented high-risk factors of interest (CHF, COPD, and/or positive fluid balance) as defined for the historical control cohort
3. The modified RSBI must be between 58-105
4. Patient must successfully complete spontaneous breathing trial and be determined eligible for extubation
5. Patient must not have extubated themselves
6. The patient must have no other contraindication that would preclude the postextubation protocol (e.g., facial trauma, tracheotomy, or any other reason that would preclude use of BiPAP or HFNC)
7. The patient must not be undergoing terminal extubation or placed on comfort care

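### Section 6.2's description of controls does not match the shared eligibility list in Section 6.3, and the mix of CHF/COPD and fluid-balance-only patients is adjusted for only if it differs significantly

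*Combined protocol and SAP*

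**What the plan says.** **Section 6.2 (Study Groups).** Controls have "documented presence of one or more chronic cardiac or pulmonary conditions" and must also "meet all inclusion criteria outlined below". The sentence on the interventional group names no chronic condition; it refers only to consent and to meeting the eligibility criteria.

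**Section 6.3.1 (controls), inclusion item 2.** The heading is "Chronic cardiac or pulmonary condition". Three bullets follow: COPD, CHF, and "Positive fluid balance, defined as a positive number when calculating fluid input minus fluid output over the approximate 24-hour-period prior to extubation". No minimum volume is set, and the text does not say whether one bullet is enough.

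**Section 6.3.2 (prospective group), day-of-extubation item 2.** The requirement is "Documented high-risk factors of interest (CHF, COPD, and/or positive fluid balance) as defined for the historical control cohort".

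Both groups also need a modified RSBI of 58–105.

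**Section 7.1.1 (primary analysis).** The logistic model for 72-hour reintubation includes as covariates those demographic and baseline characteristics that are statistically significant. Section 7.1 sets the threshold at p ≤ 0.05.

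**The concern.** Section 6.2 and Section 6.3.1 give different pictures of who can be a control. A 24-hour fluid balance is not a chronic condition, so a person working from Section 6.2, or from the item 2 heading alone, could leave out patients whose only qualifying factor is fluid balance. Section 6.3.1 gives this some practical weight: a high-risk subset is first extracted from the institutional quality list, and only then screened against the listed criteria. That first step does not say what high-risk means.

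The second issue remains however the wording is resolved. The list admits two kinds of patient: those with CHF or COPD, and those with neither but with a positive balance. Controls are drawn at random from a 2019 list, while intervention patients come from those whose representative consented. Nothing in the design holds the mix equal. If the two kinds of patient differ in reintubation risk, a different mix confounds Aim 1, and a significance rule applied to 40 and 80 patients can miss an imbalance large enough to matter.

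**Working it through.** **Step 1. Who qualifies under each section**

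| Patient, with RSBI in range | 6.2 wording alone | 6.3.1 item 2 (controls) | 6.3.2 item 2 (intervention) |
|---|---|---|---|
| CHF or COPD | yes | yes | yes |
| Neither, positive fluid balance | no, if chronic is taken literally | yes, if the bullets are alternatives | yes |

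Section 6.2 defers to the detailed criteria, and Section 6.3.2 takes its definition from the control cohort. Read together, the two groups share one list, and the difference created by the eligibility rule is zero. What remains is a discrepancy of wording.

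**Step 2. Can a difference in mix escape adjustment?**

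The group sizes, 40 and up to 80, are in Sections 5 and 6.2. The fluid-only shares are not in the documents. Assume 40% of intervention patients (16/40) and 25% of controls (20/80).

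- Pooled share = (16 + 20)/120 = 0.30. The smallest expected count is 40 × 0.30 = 12, so Section 7.1 calls for the chi-square test.
- SE = √[0.30 × 0.70 × (1/40 + 1/80)] = √0.007875 = 0.0887.
- z = 0.15/0.0887 = 1.69; uncorrected chi-square = 2.86; p ≈ 0.09.

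Since p > 0.05, entry route would not enter the model, despite a 15-point imbalance.

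**Step 3. What that does to the crude comparison**

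Assume no treatment effect. For CHF/COPD patients take 35%, the low end of the 35–67% that Section 3.2 gives for patients aged 65 or over with severe chronic disease. For fluid-only patients take 13% (midpoint of the 12–14% in Section 3.2 for planned extubation generally) to 23% (the higher arm of the high-risk randomised trial cited there).

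Group rate = 0.35 × (1 − f) + r × f, where f is the fluid-only share and r the fluid-only rate.

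| r | Controls, f = 0.25 | Intervention, f = 0.40 | Difference |
|---|---|---|---|
| 13% | 0.2625 + 0.0325 = 29.5% | 0.210 + 0.052 = 26.2% | 3.3 points |
| 23% | 0.2625 + 0.0575 = 32.0% | 0.210 + 0.092 = 30.2% | 1.8 points |

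Equivalently, the shift is 0.15 × (0.35 − r). It favours the intervention here only because the assumed excess of fluid-only patients is in that group. With the shares reversed, it would go the other way.

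**Step 4. The contrast if Section 6.2 overrode Section 6.3.1**

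This applies only on that reading. With all controls CHF/COPD at 35% and f = 25%, 50% or 75% in the intervention group, the same formula gives intervention rates of 29.5%, 24.0% and 18.5% (r = 13%) or 32.0%, 29.0% and 26.0% (r = 23%). The unadjusted odds ratios against 35% are 0.78, 0.59 and 0.42, or 0.87, 0.76 and 0.65.

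**The case against.** A reader might infer that controls must have chronic disease while intervention patients need not, so that controls are sicker by design and Aim 1 is biased toward the intervention. The documents do not support this. Section 6.2 hands over to the criteria that follow it, Section 5 also points to Section 6.3 for the detail, and the closing clause of the Section 6.3.2 item ties the intervention criterion to the control definition. The odds ratios of 0.42–0.87 in Step 4 therefore describe a strained reading. Even there, they are unadjusted. With no fluid-only controls, 10/40 fluid-only intervention patients against 0/80 gives a Fisher p of about 7 × 10⁻⁶, so entry route would enter the model if it were among the baseline characteristics tested.

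A reader might also infer that fluid-only patients dilute the population so far that the baseline-rate aim fails. That too goes beyond the text. Section 3.2 names both positive fluid balance and an RSBI above 58 as reintubation risk factors, so such a patient carries both, and Section 3.1 offers the elderly and chronically ill as examples. The breadth of the list applies to both groups and bears on how the rate is interpreted, not on between-group bias.

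The assumed rates can be challenged as well. The 35% is for older patients with severe disease, while eligibility starts at age 18 with any documented history. The 13% is for planned extubations in general and probably understates risk at RSBI 58–105. Both push the contrast upward.

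Finally, the data collection tools (Appendices A and F) are not available here, so it cannot be said that the qualifying factor goes unrecorded.

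What survives is narrower. The wording is inconsistent, and the plan's adjustment rule does not guarantee control of entry route when the imbalance is moderate.

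**Conclusion.** The point holds in two limited parts. First, Sections 6.2 and 6.3.1 need reconciling, because a literal use of Section 6.2 would screen controls more narrowly than intervention patients. Whether that would happen cannot be determined from the documents. Second, on the shared list, the significance rule can leave a real difference in entry route unadjusted. The illustration gives a shift of about 2–3 percentage points in the crude 72-hour difference. It rests on an assumed 40% versus 25% split and on assumed rates of 35% versus 13–23%. The rates are borrowed from populations that do not match either stratum and probably overstate the gap. The direction depends on which cohort has more fluid-only patients. This is a modest, avoidable source of confounding in a non-randomised comparison, not evidence that the eligibility rules are biased.

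**What to change.** 1. State one identical list for both groups, worded as one or more of COPD, CHF, or positive fluid balance as already defined. Cite it from Section 6.2, and use it to build the high-risk subset from the quality list. Give the fluid item a heading other than chronic condition.
2. Code entry route for every patient: CHF/COPD, or positive fluid balance only.
3. Include entry route as a covariate in the Aim 1 logistic model whatever its p-value.
4. Report 72-hour reintubation by entry route and group, descriptively.

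The cost is a wording change, one model degree of freedom and imprecise stratum rates. The information is already assessed to establish eligibility. Stratifying the random draw of controls on entry route is optional: it would improve balance, but matching the enrolled mix would delay the draw until that mix is known.
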